4.4. ENDPOINTS

PRIMARY ENDPOINTS

Differences between the intervention and comparison groups in changes in the frequency and quality of preventive care from their reported usual shared care to 3-months:

1. Increased % of consumers for whom each health risk is measured and recorded over the preceding 3 months*
2. Increased % consumers who have been vaccinated against influenza over the preceding 3 months
3. Decreased % consumers with high CVD risk who have not received a prescription for either an anti-hypertensive or lipid lowering drug.
4. Increased % consumers who report advice/referral for smoking cessation, diet education and physical activity over the preceding 3 months.

* Health risks are itemised in Table 3.

SECONDARY ENDPOINTS

Differences between the intervention and comparison groups in changes from their reported usual shared care to 3-months:

5. Increased % MHS consumers have a care plan (GPMP and TCA) in last 3 months
6. Increased consumer rating of extent to which providers (MH & GP) are working to a common care plan in the past 3 months
7. Improved quality of communication between MHSs and GPs in last 3 months
8. Reduced number of ED attendances and hospitalisations in last 3 months
9. Increased number of visits to GP in last 3 months
10. Improved consumer experience of providers (MH & GP) working to a common (shared) care plan in the past 3 months (qualitative analysis)
11. Increased scores on Domain 1 (Feeling understood and supported by healthcare providers) and Domain 7 (Navigating the healthcare system) of the Health Literacy Questionnaire
12. Increased score on Patient Activation Measure (PAM-13)
13. Improved diet and physical activity behaviours
14. Reduced Absolute Cardiovascular Disease Risk score **
15. Reduced diabetes risk score using AUSDRISK ***
16. Improved levels of most recently recorded results from health risk screening*
17. Reduced costs of hospitalisations in last 3 months
18. Reduced out of pocket costs of participants
19. Improvements in Quality of Life as assessed by the EQ5D-5L.

* Health risks are itemised in Table 3.

** Information needed for CVD risk score is provided in Table 4

*** Information needed for AUSDRISK score is provided in Table 5.

Table 3 Health risks

Health risks	Units/options	Normal range/goals
Systolic & diastolic blood pressure (BP)	mmHg	<130/85 mm Hg

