5.4 CONFOUNDERS

Any baseline differences between clients seen by intervention and comparison teams in demographic or socioeconomic characteristics and mental health condition may act as potential confounders. These will be assessed in the analysis and, if necessary, adjustment made in analyses.

Another potential confounding factor could be that patients will accumulate around the GPs with the most engagement in the study who have the shared eMR (electronic medical record) installed early on. MHS case coordinators will be asked to monitor whether any consumers have changed GPs as a result of the trial and inform the study investigators if this happens. We cannot stop consumers from changing GPs, but we can only monitor if this happens. Our experience with this consumer group is that changing GPs is unlikely unless a consumer is dissatisfied with their existing GP.

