7. OUTCOMES AND DATA SOURCES

Table 9 Outcomes and their data sources

Concept	Primary Outcomes	Data source
1 Preventive care	GP-recorded screening of health risks 6-month period post-intervention* (May-October 2023) compared with the 6-month periods: 
 • Pre-intervention (November 2022-April 2023) • In the previous year (May-October 2022) 
*"intervention" = shard care plan in Inca (May-June 2023)
	GP records
	GP-recorded prescription of antihypertensive or lipid lower medications 6-month period post-intervention* (May-October 2023) compared with the 6-month periods: 
 • Pre-intervention (November 2022-April 2023) • In the previous year (May-October 2022) 
*"intervention" = shard care plan in Inca (May-June 2023)
	GP records & HealtheNet
	Consumer-reported advice/referral from GP for smoking cessation, diet and physical activity in last 6 months	Consumer survey

Concept	Secondary Outcomes	Data source
1 Preventive care	GP-recorded care plans: GPNP and Team Care, mental health 6-month period post-intervention* (May-October 2023) compared with the 6-month periods: 
 • Pre-intervention (November 2022-April 2023) • In the previous year (May-October 2022) 
*"intervention" = shard care plan in Inca (May-June 2023)
	GP records
2 Integration of care	Consumer assessment of extent to which providers (MH & GP) are working to a common care plan in last 6 months	Consumer survey
	Provider reported quality of communication between MHSs and GPs in last 6 months	Provider survey and qualitative interviews

Concept	Secondary Outcomes	Data source
3 Health service use	ED use and hospitalisations for primary care preventable conditions and other conditions 6-month period post-intervention* (May-October 2023) compared with the 6-month periods: 
 • Pre-intervention (November 2022-April 2023) • In the previous year (May-October 2022, to check for seasonal effect) 
*"intervention" = shard care plan in Inca (May-June 2023)
	SLHD eMR (Appendix 14), Integrated Care Outcomes Database (ICOD)

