8.2. PROVIDE A DETAILED ANALYSIS PLAN

Quantitative analysis

The fidelity and tailoring of the intervention to participants' needs will be assessed by analysing records, provider and consumer interviews 3 months after their usual shared care appointments. We will compare outcomes over 3 months after intervention between SHAReD intervention and comparison groups with linear or generalised multi-level mixed models including age, sex and key independent variables that are found to be significantly different between groups at baseline. Intra-class correlations will be calculated to compare the amount of variance associated with design features such as individual participants nested within care coordinators who are nested within community mental health teams, and those same participants are also nested within GPs who could also be nested within medical centres, before selecting random effects for these statistical models. As well as an analysis of completers (defined as those consumers, care coordinator and GP who

consented and are engaged in shared care), an intention to treat (ITT) analysis will also be included for this project. For the ITT analysis, those who drop out of the study (defined as consumers who were discharged of shared care or who withdrew consent) will be treated using a variety of sensitivity analyses including multiple imputation for the missing values on key measures resulting from them dropping out of the study. Sensitivity analyses will assess unmeasured variation.

Qualitative analyses

This will evaluate the experience of participants, carers and providers, barriers to implementation, conditions for sustainability and translation. Qualitative data will be managed and coded using NVivo 11 analysis software (QSR International). Two researchers will review each transcript and develop coding aligned with the Theoretical Domains Framework and Normalisation Process Theory.^{25,26} Coding will be predominantly deductive but inductive coding will also be applied to detect new and emerging themes.

Data combining and cost analyses

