Additionally, it will be informative to measure the healthcare costs of SMI from the viewpoint of the SLHD/NSW health system, expressed as average total costs of SMI treatment per person under the alternative care situations. The SHAReD care group may be broken down into several subgroups for the analysis, and based on the degree to which they completed the intervention (e.g. their adherence to the shared e-plan, how many times they were engaged with the essential components

of the intervention and what they received, the quality of SHAReD care delivery, and participant acceptability and responsiveness to the intervention).²⁷ All costs will be expressed in 2023 Australian dollars.

Econometric methods commonly used to address issues associated with healthcare usage and cost variables such as problems of heteroscedasticity and skewness will be applied in this study.²⁸ These methods will be used to estimate the total (and differences in/incremental) costs (and costs specific to single and multiple health conditions, health risks, cardiometabolic outcomes) associated with the SHAReD care situation versus usual care adjusted for several participant and system-level characteristics. Various econometric methods will be explored such as log-transformed ordinary least squares models, GLMs (and may be those for repeated measures/panel data too) and survival (duration) models, with “goodness of fit” and other statistical measures used to make decisions about the models.²⁹

There may be missing data especially from the survey or general practice or as a result of merging data. This will be addressed by multiple imputation in the analysis.

To address confounding, variables with baseline differences between SHAReD intervention and usual care will be included in the final multivariate regression analysis.

To manage any risk that merging databases of non-identifiable data could subsequently result in the individuals being identified, data will be de-identified after combining the SLHD eMR data and costs with consumer survey data and stored securely (see section 12 of protocol). Only data with more than five individual responses will be released.

Costing component and the economic evaluation

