9.2 Consumer quantitative interviews

Survey interviews will be conducted with both intervention and comparison consumers at baseline and 3 months after their usual shared care (or 30 June 2023 if they did not have a shared care plan). The interview schedule components and their sources are summarised in Table 9.

Table 10 Sources of questions in the consumer survey

Outcomes	Source of questions
Consumer-reported advice/referral from GP for smoking cessation, diet and physical activity in last 6 months	Questions developed by CPHCE in previous research ^{32,33}
Consumer assessment of extent to which providers (MH & GP) are working to a common care plan in last 6 months	Question developed by CPHCE, informed by research on interprofessional teamworking in primary and community care settings ³⁴
Health literacy (Feeling understood and supported by healthcare providers)	Health Literacy Questionnaire (HLQ) (Domain 1) ³⁵
Current health risk behaviours	Questions developed by CPHCE
Absolute Cardiovascular Disease Risk	Australian Absolute Cardiovascular Disease Risk ³⁷
Diabetes risk	AUSRISK ³⁸
Quality of life	EQ5D-5L ^{28,29}
Costs	Out-of-pocket costs

Accommodation of mental illness: Interviews will be usually conducted by telephone or video conferencing. Carers or support workers will be asked to assist if the participants agree. The interview questions will use plain English and graphic images. Where participants are judged by treating staff to be unable to understand or answer questions remotely the interviews will be conducted in person, with arrangements to ensure the safety of the consumer and research team. In person interviews will be conducted in a location such as health service and respecting social distancing in accordance with the COVID-19 plan of the SLHD. Carers or support workers will be asked to assist if the participant wishes.

The study procedure is flexible allowing interviews to be postponed if the participant is distressed or acutely ill. If participants become distressed during the interview, researchers will provide basic support and inform the care coordinator that the consumer was feeling distressed and might need follow up. If this happens out of hours, the researcher will ask the consumer if there is somebody they should call who can provide support e.g., support worker, GP or carer. If the researcher is concerned about a participant's safety out of hours, they will contact the mental health line [name].

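### Section 8.2 chooses covariates beyond age and sex by baseline significance and names no pre-period outcome term, although the endpoints are differences in change

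*Protocol*

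**What the plan says.** Section 8.2 (quantitative analysis) sets the main comparison: "We will compare outcomes over 3 months after intervention between SHAReD intervention and comparison groups", using linear or generalised multi-level mixed models "including age, sex and key independent variables that are found to be significantly different between groups at baseline". Age and sex always enter. Any other covariate enters only if it is flagged. The paragraph names no baseline or pre-period value of the outcome.

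Two other places use looser versions of the same idea. For the cost analyses, section 8.2 says that "variables with baseline differences between SHAReD intervention and usual care will be included in the final multivariate regression analysis". Section 5.4 says of baseline differences in demographic or socioeconomic characteristics and mental health condition: "These will be assessed in the analysis and, if necessary, adjustment made in analyses". Neither mentions significance.

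The endpoint is worded differently. Section 4.4 defines the primary endpoints as "Differences between the intervention and comparison groups in changes in the frequency and quality of preventive care". Table 9 sets the record-based primary outcomes for May to October 2023 against two earlier windows, November 2022 to April 2023 and May to October 2022. For the survey outcomes, section 9.2 says: "Survey interviews will be conducted with both intervention and comparison consumers at baseline and 3 months after their usual shared care".

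Models for change do appear in section 8.2, but elsewhere: difference-in-difference and repeated-measures models for quality of life, and repeated-measures models as a possibility for costs. The synopsis adds baseline predictors to the models, but to study the effect of those characteristics on outcomes, not to define the treatment comparison.

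**The concern.** A baseline p-value measures how unequal the arms are relative to sampling error. It does not measure how strongly a variable predicts the outcome. A prognostic variable with a moderate imbalance is left out, while an irrelevant one with a chance imbalance is put in. The final model is then unknown until the data are seen.

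The design makes this more than a formality. Four teams are randomised, two per arm, by coin flip within sector (section 4.1), so sizeable differences between arms are plausible. The earlier value of the same outcome is an obvious candidate covariate, and it is already due to be collected. As written, it would enter the main models only if it counted as a key independent variable and also differed significantly. A comparison of post-intervention values alone also does not estimate the difference in change that section 4.4 promises.

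**Working it through.** **The plan's own figure.** Inputs from section 8.1: 30% against 50%, alpha 0.05 (two-sided assumed), power 0.80.

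n = (0.3×0.7 + 0.5×0.5) × (1.96 + 0.8416)² / 0.20² = 90.3, so 91 per group, as stated. A design effect of 2 gives 182 per group and 364 in total, against the stated 180 and 360. The sample size reproduces and is not in dispute. Its formula compares two independent proportions and contains no baseline term.

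**Step 1: what the test can flag.** Smallest significant difference with 180 per arm, conventional test without clustering: 1.96 × √(2p(1−p)/180).
- p = 0.3: 1.96 × √(0.42/180) = 9.5 points
- p = 0.5: 1.96 × √(0.50/180) = 10.3 points

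Section 8.2 does not say which test is meant. One that allowed for a design effect of 2 would put the cut-off higher (√2 × 9.5 = 13.4 points at p = 0.3) and flag fewer variables.

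**Step 2: how large imbalances are by chance.** Assumption: the design effect of 2 sits at team level, with 90 per team, and applies equally to the baseline variable. Then 1 + 89 × ICC = 2, so ICC = 1/89 = 0.011. The SD of the arm difference is √2 × √(2p(1−p)/180):
- p = 0.3: 6.8 points
- p = 0.5: 7.5 points

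**Step 3: how often a moderate imbalance goes unflagged.** P(5 points < |d| < cut-off), normal approximation:
- p = 0.3: 2 × [Φ(9.5/6.8) − Φ(5/6.8)] ≈ 0.30
- p = 0.5: 2 × [Φ(10.3/7.5) − Φ(5/7.5)] ≈ 0.34

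At either prevalence the conventional test is triggered with probability 2 × [1 − Φ(1.96/√2)] = 0.17, so the variable is left out in about 83% of trials.

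**Step 4: effect on the estimate.** With equal variances before and after, the adjustment coefficient equals the pre/post correlation r, so the shift that adjustment would remove is r × imbalance. The documents give no r; 0.3 to 0.5 is assumed.
- Low end: 0.3 × 5 = 1.5 points (1.5/20 = 7.5% of the target)
- High end: 0.5 × 10.3 = 5.2 points (5.2/20 = 26%)

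**Step 5: precision.** Adjustment removes about r² of the individual-level variance: 0.3² = 9% to 0.5² = 25%. This is a linear-scale approximation.

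**Step 6: simulation of the rule.** No treatment effect, four teams of 90, 30% rate, ICC 0.011, team effects persisting between periods, 8,000 runs per correlation. The pre-period outcome is the only candidate covariate, and the test ignores clustering. SD of the estimated effect, in points:

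| r | never adjust | adjust if significant | always adjust |
|---|---|---|---|
| 0.3 | 6.8 | 6.1 | 5.7 |
| 0.5 | 6.8 | 5.7 | 4.8 |
| 0.7 | 6.8 | 5.3 | 3.8 |

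The mean estimate was within about 0.1 point of zero in every cell. Because team effects are assumed to persist, the gains here exceed the r² of step 5.

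**The case against.** Several limits on the point are fair and stand.

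- **Silence is not exclusion.** Section 8.2 does not define its key independent variables and does not forbid a baseline term. A statistical analysis plan that is not shown may add one. What remains is what the Protocol does state: selection by significance, and a post-intervention comparison that does not match section 4.4.
- **The significance rule appears once.** The cost-analysis paragraph and section 5.4 are looser, and age and sex are fixed throughout. It would be wrong to say that all covariates are chosen by testing.
- **The ICC of 0.011 is not the plan's.** The Protocol gives only a design effect of 2 and does not say at which level. Section 8.2 lists care coordinators, teams, GPs and medical centres.
- **The pre/post correlation is unknown.** Nothing in the documents shows that the earlier outcome is the strongest predictor. Table 7 includes an annual health check, so a check in one six-month window might even make one in the next less likely.

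A reader might also infer that an unflagged imbalance of 5 to 10 points passes in full into the estimate, which would be a quarter to a half of the target. That needs an adjustment coefficient of 1, which the documents do not support. At 0.3 to 0.5 the shift is the smaller one in step 4.

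**Conclusion.** The point holds as a stated but inferior covariate rule, and as a mismatch between the main model in section 8.2 and the change endpoints in section 4.4. It is an improvement that should be made, not an error that invalidates the trial.

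Its size is moderate. In about 30% to 34% of trials, an imbalance of 5 to about 10 points in a binary baseline variable would go unadjusted. If that variable is the earlier outcome, the estimate moves by about 1.5 to 5 points. These figures rest on the design effect sitting at team level with 90 per team, and on a correlation of 0.3 to 0.5. The cut-offs of 9.5 and 10.3 points need only the stated 180 per arm, a conventional 5% test, and prevalences of 30% and 50%.

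A reader might conclude that the rule biases the treatment effect. Averaged over randomisations the simulation shows no bias. The harm is error conditional on the one allocation actually drawn, wider uncertainty than always adjusting at every correlation tried, and a model that depends on the data.

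**What to change.** In section 8.2, delete selection by baseline significance (main models) and by baseline difference (cost analyses), and bring section 5.4 into line. Fit each outcome model with a set fixed in advance:

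- the pre-intervention value of the same outcome: the Table 9 pre-period for record outcomes, with the previous-year window where available, and the baseline survey value for survey outcomes;
- age and sex;
- sector, the stratification factor in section 4.1.

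A repeated-measures model with a group-by-period term is an alternative that also matches section 4.4. State whether the arms share a common baseline mean. If they do, it behaves much like the adjusted model. If not, it is a difference in differences, with individual-level variance 2(1 − r) relative to the unadjusted comparison: 1.4 at r = 0.3 and 1.0 at r = 0.5, against 1 − r² = 0.91 and 0.75 for adjustment.

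Add mental health condition only if a planned source holds it. Section 5.4 names it as a potential confounder, but no data item is listed, the interviews will not seek illness history (section 5.3), and clinic files will not be reviewed (section 6.4).

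The cost is wording and minor analysis work. Pre-period GP records may be missing for consumers whose GPs decline but who stay in the study (sections 4.5 and 5.3). The multiple imputation already planned in section 8.2 can be extended to these values.

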

Statistical considerations
	
Sample size calculation Assuming 20% change, a sample size of 91 per group is required to detect a change from 30 to 50% in primary outcomes based on $\alpha = 0.05$, $1-\beta = 0.8$. Assuming a design effect due to clustering of 2, a total sample of 360 is required (180 in each group).
 
Analysis plan For analysis of differences between the intervention and usual care alternatives, linear or generalised multi-level mixed models will be estimated depending on the type of outcome in question. Intra-class correlations will be calculated to compare the amount of variance associated with design features as individual participants are nested within care coordinators who are nested within community mental health teams, and those same participants are also nested within GPs who may also be nested within medical centres, which will occur before selecting random effects for these models. As well as an analysis of completers, defined as those consumers, care coordinators and GP triads that complete an online shared care plan, an intention to treat (ITT) analysis will also be completed for this study. For the ITT analysis, those who have dropped out will be treated using a variety of sensitivity analyses. Further, baseline predictors and intervention features of both the SHAReD (e-shared care) and usual care situations will be added to multi-level models to identify effects of these characteristics on outcomes. Qualitative analyses (predominantly deductive but inductive coding will also be applied to detect new and emerging themes) will also be undertaken. All relevant costs such as implementation costs and healthcare usage [hospitalisations, GP care, specialists, allied health, and prescribed medication, and the multiple outcomes such as interactions with the health system, engagement, preventive tests undertaken, clinical measures and quality of life for participants in the intervention and usual care groups will be quantified, and tests of significance will be undertaken on these data. These results will be used in a cost-consequence analysis (CCA). A comprehensive within-trial cost-effectiveness study will also be conducted provided effectiveness has been demonstrated, with the main effects/benefits consisting of satisfactory completion of an online shared care plan, reduction in consumer cardiometabolic risk, and avoiding unplanned hospitalisations. A cost-utility evaluation will be conducted if effectiveness in relation to quality of life has been demonstrated, to provide a ranking of the alternatives (e-shared care, usual care) on the basis of the amount of resources (costs) used to gain an extra quality adjusted life year (QALY) by receiving the SHAReD intervention. All the necessary effects/benefits and costs (direct medical, consumer costs for medical care and any indirect costs) will be identified, counted and valued using established methods. A range of incremental cost-effectiveness ratios (ICERs) will be calculated such as the incremental cost for an extra QALY gained, cost for an unplanned hospitalisation that was avoided. Sensitivity analysis will be conducted and some results presentations graphically.

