patient data collection using medical record numbers (and eMR) and associated SLHD costings during the study. Costs attributable to the research will not be considered. Estimates of how the work of clinicians (and thus costs) has changed from the situation without the SHAReD intervention will also be explored during the focus groups. Variations in healthcare usage (such as hospitalisations and other medical treatment sought) and costs occurring later in the study (and up to 3 months post completion of the intervention) will be sought from SLHD eMR reports and the SLHD Performance Unit for cost of ED presentations and hospitalisations. The mean costs in the SHAReD intervention and usual care groups will be compared in addition to the mean health effects/benefits such as the care plan completion rate, quality of care received, clinical metrics, hospital admissions (and readmissions), hospital length of stay, and score on the utility-based and disease-generic quality of life measure (EQ5D-5L).^{30,31}

Having data on both the healthcare resource utilisation (costs) and health effects/benefits for the different groups will allow us to undertake a detailed cost-consequence analysis (CCA) – a first step for the economic assessment. CCA is a widely used form of economic assessment and recommended for reporting on health interventions with significant complexity and when there are multiple effectiveness measures such as programs/models of care seeking to address a range of clinical outcomes (Drummond et al 2005), and broad-reaching programs that have a range of health and non-health related effects needing to be quantified and assessed (NICE 2017). For this initial step of the economics work, the relevant costs and multiple outcomes will be calculated and presented in a disaggregated way which enables decision-makers to assess the relative importance of each component to the context they face. The comparator will consist of those consumers who did not receive the SHAReD intervention. Descriptive analysis will be used to estimate the total and mean costs (and standard deviations) associated with the intervention and usual care, as well as the effectiveness information (outcomes) and reported in a disaggregated manner.

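### Cost subgroups defined by completion of the intervention exist in the SHAReD arm only; contrasting them with usual care can show false savings or false excess costs, and the cost comparator is worded by receipt instead of allocation

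*Protocol*

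**What the plan says.** All of this is in Protocol section 8.2 unless stated otherwise.

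- *Data combining and cost analyses* sets out to measure health care costs, "expressed as average total costs of SMI treatment per person under the alternative care situations". It then says that the SHAReD care group "may be broken down into several subgroups for the analysis, and based on the degree to which they completed the intervention". The examples given include "their adherence to the shared e-plan, how many times they were engaged with the essential components" of the intervention, delivery quality, acceptability and responsiveness. No matching split of usual care is described.
- The next paragraph has the cost models estimate total and incremental costs "associated with the SHAReD care situation versus usual care adjusted for several participant and system-level characteristics". For confounding, "variables with baseline differences between SHAReD intervention and usual care will be included in the final multivariate regression analysis".
- The cost window is May to October 2023. The exposure, having a plan in Inca, is dated May to June 2023.
- *Costing component and the economic evaluation* keeps a whole-group comparison: "The mean costs in the SHAReD intervention and usual care groups will be compared". For the cost-consequence analysis, however, it defines the comparator as consumers who have not received the intervention.
- Section 5.3 (item 9) says that if a GP declines, that GP's patients get no access to the online tool but can still give baseline data and are followed up.

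**The concern.** Completion is observed after allocation. A consumer who is admitted or acutely unwell early in the window may both cost more and be less able to keep the GP visits that count as engagement. Because the exposure months lie inside the cost months, the cost being measured can influence the subgroup a consumer falls into.

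Usual-care consumers have no e-plan to adhere to. The only available reference for a high-completion subgroup is therefore the whole usual-care arm, including people who would not have engaged. Such a contrast asks whether engaged consumers cost the same as average consumers, not whether the intervention changes cost. Adjusting for variables that differ between arms at baseline does not deal with selection within one arm.

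The comparator wording adds to this. Read literally, a consumer of an intervention team whose GP declined did not receive the intervention and could be counted in the comparator. At stake is the answer to research question 4 (section 3) and to hypothesis 4 (section 2), which predicts lower costs.

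**Working it through.** **Figures in the plan.** The Protocol gives no figure for the cost analysis. Its sample size supplies the arm size and design effect used here. For 30% against 50%, two-sided 0.05 and 80% power: (1.960 + 0.842)² × (0.3×0.7 + 0.5×0.5) / 0.2² = 7.849 × 0.46 / 0.04 = 90.3, so 91 per group, as stated. With a design effect of 2, 91 × 2 × 2 = 364, against the stated 360. Follow-up is 500 × 0.8 = 400, or 200 per arm if the arms are equal.

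**Assumed inputs (not in the documents).**
- The true intervention effect is zero.
- Engagement and cost (in SD units) are jointly normal, with higher engagement going with lower cost at correlation ρ = 0.1, 0.2 or 0.3.
- The SHAReD arm is split in thirds by engagement, and the top third is compared with all of usual care.

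**Formulas.** For the top fraction f = 1/3, the cut-point is c = 0.431 and λ = φ(c)/f = 1.091.
- Expected difference: b = −ρλ.
- Variance of cost within the top third: v = 1 − ρ²λ(λ − c) = 1 − 0.720ρ².
- SE = √(v/66.7 + 1/200), multiplied by √2 for a design effect of 2.
- Two-sided rejection: Φ(−1.96 − b/SE) + 1 − Φ(1.96 − b/SE).

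**Worked case, ρ = 0.2.** b = −0.218; v = 0.971; SE = √(0.01457 + 0.005) = 0.140, or 0.198 with the design effect. Then b/SE = −1.10, and rejection is Φ(−0.86) + 0.001 ≈ 0.197.

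| ρ (assumed) | b (SD) | Rejection, independent individuals | Rejection, design effect 2 |
|---|---|---|---|
| 0 | 0 | 5.0% | 5.0% |
| 0.1 | −0.11 | 12.1% | 8.5% |
| 0.2 | −0.22 | 34.5% | 19.7% |
| 0.3 | −0.33 | 66.0% | 38.9% |

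**Check by simulation** (20,000 trials per ρ, independent individuals, no effect). The top third showed a false saving in 12.2%, 35.1% and 66.1% of trials for ρ = 0.1, 0.2 and 0.3. The bottom third showed a false excess cost in 12.1%, 34.4% and 65.5%. Whole arm against whole arm rejected in 5.1% to 5.4% for ρ from 0 to 0.3. If engaged consumers cost more, the signs reverse.

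**Passages side by side.** Section 5.3 keeps intervention-team consumers without the tool in follow-up. The cost-consequence comparator in section 8.2 is worded by non-receipt. Together they leave it open in which group these consumers' costs are counted.

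**The case against.** The strongest reply is that the criticised contrast is not written. The split is optional, no sentence says that a subgroup will be tested against usual care, and the listed items could serve a description of fidelity. Whole-group comparisons of mean cost are kept, the planned ICERs compare the SHAReD group with the usual-care group, and the section includes an intention-to-treat analysis. All of this stands. What remains is that the split sits in a paragraph about cost under the alternative forms of care, directly before the incremental cost models, and nothing confines it to description.

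A second reply is that the models are covariate-adjusted and that pre-intervention and previous-year costs are available, which could absorb some selection by severity. That is fair, but the stated adjustment rule is tied to differences between arms, and no earlier period captures an admission within the exposure months.

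Third, section 5.1 (criterion 4) makes GP consent an entry condition in the intervention group, which might seem to remove consumers of declining GPs. Section 5.3 nevertheless follows them up, so the comparator still has to say where they belong.

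A reader might also infer that the synopsis distorts the arm effect, since "baseline predictors and intervention features of both the SHAReD (e-shared care) and usual care situations will be added to multi-level models". The documents do not support that. The sentence covers features of both forms of care, its stated purpose is to identify the effects of those characteristics, and it does not say that the model reporting the arm effect will contain them.

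**Conclusion.** The point holds in limited form. The Protocol permits a grouping made after allocation, in one arm only, within its cost comparison. It offers no safeguard against selection into engagement, and it words one cost comparator by receipt. If completion subgroups are contrasted with usual care, a difference can appear with no effect: about 0.11 to 0.33 SD for the top third, with 8.5% to 39% rejection at a nominal 5% after doubling the variance. These sizes rest entirely on assumed correlations of 0.1 to 0.3, a split in thirds and normal outcomes. They are illustrative, not predictions for this trial.

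A reader might go further and infer that the plan will find savings where there are none. The documents give no correlation and no direction. Engagement itself uses GP visits and tests, so the bias could be nil or could run towards excess cost. Nor does the split replace the whole-arm comparison. The near-5% rejection for whole arms assumes independent individuals and says nothing about the separate difficulty of having only four teams.

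**What to change.** In section 8.2:

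1. Under both *Data combining and cost analyses* and *Costing component and the economic evaluation*, state that the cost comparisons answering research question 4 are between all enrolled consumers of the teams allocated to SHAReD and all enrolled consumers of the teams allocated to usual care, whatever they received.
2. Reword the comparator of the cost-consequence analysis by team allocation.
3. State that cost by completion level is reported only as description within the SHAReD arm, with no contrast against usual care.

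This needs wording only and no new data. The cost is that completion-level results become descriptive. A complier-average estimate need not be required: with four teams as the instrument it would be very imprecise. The synopsis sentence on intervention features needs no change on this account. The change removes the selection problem but does not address the small number of clusters.
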